5.1 Exclusion Criteria

Participants must *not*:

- a) Have had one of the following exclusionary cancer types:
 - i. Non-melanoma skin cancer *only (not in combination with another type listed in the inclusion criteria above)*
 - ii. Brain cancer
 - iii. Eye cancer
 - iv. Any form of pediatric cancer *(if the pediatric cancer is the only cancer diagnosis the patient has had)*
- b) Currently be undergoing primary treatment for their cancer
- c) Have had inpatient treatment for severe mental illness in the past 12 months or have overt signs of psychopathology (i.e. psychosis) and/or suicidality at the time of screening.
- d) Be experiencing active alcohol dependence or have had inpatient treatment for alcohol abuse within the past 12 months.
- e) Be experiencing active substance dependence or have had inpatient treatment for substance abuse within the past 12 months.
- f) Have any other medical conditions resulting in a predicted life expectancy <12 months.

5.2 Recruitment and Retention Methods

For this 1-year pilot, we plan to recruit 30 Latino HIV+ cancer survivors who are sexual minority men. By working with a variety of UM and UM-affiliated groups, including Sylvester Comprehensive Cancer Center as well as our external partners we hope to enroll HIV+ cancer survivors of diverse backgrounds, in terms of age, education, and socioeconomic status. We acknowledge that recruiting this many patients from such a unique population and within the proposed timeframe may present several challenges. However, study staff will capitalize on their working relationships with University of Miami Medicine affiliates and their connections to community partners.

Screening and Recruitment: Participants for this pilot will be recruited remotely (online or by phone). For this study, staff will utilize these primary avenues for participant recruitment: 1) the University of Miami Medicine system and its University of Miami affiliates (e.g., Sylvester Comprehensive Cancer Center, consent to contact lists from other University of Miami investigators), 2) online advertising via social media, and 3) collaboration with external partnering community-based organizations.

University of Miami Medicine and its UM affiliates (UHealth Clinics, UM Consent to Contact Database, or Other UM Investigators' Consent to Contact Lists)

A partial HIPAA waiver is requested for screening and recruitment purposes (See section 12.1.3 for HIPPA Waiver). Such a waiver is appropriate for the following reasons:

- a) This study is of no more than minimal risk to prospective patient/participants, as their participation simply involves undergoing a psychosocial intervention and providing questionnaires and does not utilize drugs, medical devices, or medical procedures of any kind.
- b) Personal identifiers obtained via the report will be used to determine patients' eligibility for enrollment only and will be destroyed as soon as possible after the determination of eligibility is made.
- c) All other personal health information (PHI) collected from patients will be obtained by self-report only. For the purpose of this pilot, study staff is *not* requesting access to enter patients' electronic medical records beyond the pre-screening.
- d) Given the timeline of the recruitment for the project (less than 1 year), it would be impracticable for the study team to rely solely on direct referrals from healthcare providers to enroll the desired number of patients for the pilot (50). Conducting a chart review will enable the study team to obtain a larger number of patient names in a shorter amount of time, thus rendering the recruitment timeline feasible.

A limited amount of PHI will be reviewed from patient charts in order to pre-screen patients. Patients to be pre-screened will be determined from the scheduled list of patients on a given day within the study period in the appropriate disease teams (i.e., Infectious Diseases, AIDS Clinical Research Unit, etc.). The research personnel will review charts for the following information: whether the person is male, 18 years or older, Hispanic, speaks English, has a metastatic or non-metastatic solid tumor cancer, and is \geq 30 days post active primary treatment. Patients who are identified through UChart review will be approached through their treating physician. We will advise their treating physician and direct medical staff of the possible eligibility to our study, and further request for them to introduce our study to the patient. If the patient is interested, they will be instructed to either call us or provide their verbal consent to be contacted by the study team for screening.

We will also obtain a list of potentially eligible participants from the UM Consent to Contact Database. The following criteria will be used to generate the patient contact list: male, 18 years or older, Hispanic, speaks English, a metastatic or non-metastatic solid tumor cancer (by ICD-10/ICD-9 codes), and not receiving active treatment (by CPT codes). Additionally, we will be utilizing MyChart Research Recruitment as a tool to identify and safely communicate with participants who agreed to be contacted if they meet the initial study eligibility criteria from the EMR.

In addition, our research team will partner with other UM investigators doing work in HIV and/or cancer who have obtained informed consent from prior or current study participants to be contacted for future studies. Requesting these lists from other investigators will enable the study team to obtain a larger number of patient names in a shorter amount of time, thus rendering the recruitment timeline feasible.

After receiving the lists of potentially eligible participants, study staff will contact individuals via phone using the Consent to Contact Script. If the prospective participant declines to provide verbal consent for screening, the study team member will thank them for their time and end the call. However, if the prospective participant does provide

Confidential

verbal consent, the study team member will proceed with the screening process, giving the individual the option of completing the full screener either by phone or online. *For those screened by phone*, study staff will enter patient's responses into REDCap and confirm the prospective participants' eligibility (or lack thereof) for the study. *For those who complete the online eligibility screener* (also REDCap), study staff will confirm eligibility during a follow-up phone call.

Online Advertising via Social Media

As most individuals are now using social media, such as Facebook, Instagram, and Twitter to stay connected with friends and family, it makes sense for the study team to advertise this potential research opportunity in this manner. Those who learn of the study via Facebook advertisements or other social media, will be directed to a brief online eligibility pre-screener, the responses to which will be captured in REDCap. On other similar studies utilizing Facebook ads, staff have noted that a number of people have clicked on the pilot's Facebook ads and either "liked" them or shared them on their personal pages. However, these same individuals have not then proceeded to complete the online pre-screener.

Moving forward, study staff will send a brief message to those individuals who comment explicitly on their Facebook pages that they are interested in taking part, but who have been unsuccessful in finishing the online pre-screener. If an individual simply shares or "likes" an ad for the pilot, study staff will not message them. Same procedures will be utilized for the other social media channels. Study staff will review all completed online pre- screeners and determine whether respondents appear to meet preliminary eligibility criteria. If respondents do meet these preliminary criteria, UM study staff will call these respondents to complete the screening process by phone or online.

Partnership with External Collaborator

Potential participants may also be recruited remotely via the study team's collaboration with local community-based organizations serving LGBT individuals. These community-based organizations provide social services specifically for sexual minority men living with HIV and have longstanding relationships with university investigators. These organizations may advertise the study to their patrons. If someone who is not currently a UM patient, or who is a UM patient that has not been identified by the staff as a potential participant, calls our external community partners to inquire about general research opportunities, they will be redirected to our staff who will provide them with information about the study and ask for their verbal consent to complete the screening process by phone or online. In addition, we will recruit participants through referrals from enrolled participants. Enrolled participants will receive \$20 for every referral of a potentially eligible person (i.e., adult male with HIV and cancer).

Other avenues for participant recruitment

We will advertise this trial in online recruitment platforms (e.g., ResearchMatch) that help connect researchers with individuals interested in learning about research study opportunities. First, we will enter our inclusion criteria to generate a list of potentially eligible participants. Then, we will send a contact message to these individuals (See *ResearchMatch message*). Once the individual has authorized to release their contact information to our study team, we will call these respondents to complete the screening process by phone or online.

Financial Compensation:

Participants will receive a \$75 electronic payment (e.g., Zelle, digital gift card) at each of two assessments (baseline, post-intervention), and additional \$25 for participating in a

final interview (A total of \$175 for study participation).

6 STUDY PROCEDURES

Study staff will follow guidelines from the CTSI on e-consenting using REDCap. After consent has been obtained, study staff will instruct the participant to complete the intake questionnaire.

Intake questionnaire:

- a) **Demographics and Disease Information:** Participants will complete: a demographic survey which will include factors such as age, race, education, employment status, income, nativity, years in the US, and relationship status. Participants will also complete a disease information form, which will collect medical history relevant to their cancer and HIV diagnoses. Finally, participants will complete ACTG HIV medication Adherence measure,¹⁹ and the Barriers to HIV Care survey.²⁰
- b) **Psychosocial Factors:** Participants will complete the Coping Self-Efficacy scale,²¹ Interpersonal Support Evaluation List (ISEL),²² the Bidimensional Acculturation Scale for Hispanics,²³ and the Computer Proficiency Questionnaire (CPQ).²⁴
- c) **Intervention Outcomes:** Participants will complete: the Perceived Stress Scale (General Stress),²⁵ the Impact of Event Scale (Disease/Dual-diagnosis-related Distress),²⁶ and The Functional Assessment of Cancer Therapy scale-General (FACT-G; HRQoL),²⁷ and Medical Outcomes Study HIV Survey (MOS-HIV; HRQoL).¹⁹
- d) **COVID-19 Questions:** Participants will complete the COVID-19 Impact of the Pandemic and HRQOL in Cancer Patients and Survivors measure.
- e) **Computer Proficiency:** Measured with the Computer Proficiency Questionnaire.

Once participants complete the intake questionnaire, they will be prompted to register on the culturally-tailored SmartManage intervention website. Study staff members who have previous experience and expertise in delivering CBSM interventions to Latino populations will conduct the study intervention interactive sessions. Following the intervention, participants will be prompted to complete their exit questionnaire in REDCap.

Exit Questionnaire. For the exit questionnaire, the participants will complete all intake measures (excluding the Demographics and Disease Information) and will also complete a measure of acceptability. As standard acceptability constructs include relative advantage, compatibility, and complexity, the acceptability evaluation measure will cover ease of use of the culturally-tailored web-based SmartManage intervention, including participants' confidence in their ability to successfully complete the intervention, as well as general comfort with the intervention process.²⁸ Additionally the acceptability evaluation measure will gauge preference web-based vs. in-person interventions, as well as willingness to complete the culturally-tailored web-based SmartManage intervention again or refer a friend to the intervention. The acceptability evaluation measure will also allow participants to give open- ended comments/feedback about the intervention.

Final Interview. Participants will be asked to participate in a final interview to discuss the challenges or factors that influenced their participation in the program, the impact of the program on their health, and suggestions for improvement. The interview will be conducted by phone or videoconference, will last about 30 minutes, and will be video or

audio-recorded and then transcribed by study team members (See Final Interview Guide).

7 PARTICIPANT WITHDRAWAL

7.0 Participant Withdrawal from the Study

Although we will seek to minimize participant withdrawal, participants will be told that this study is completely voluntary and that they have the right not to participate in any intervention procedure. They also can completely withdraw from the study at any time without any negative consequences.

If, for some unforeseen reason, a situation arises in which a participant experiences more harm than good during the study, the PI may choose to withdraw this participant. Though highly unlikely, such situations could include excessive physical, psychological, or emotional suffering. Other circumstances under which participants will be withdrawn from the study may include: the participant no longer meet the eligibility criteria, providing fraudulent data, or other reasons deemed appropriate by the Primary Investigator. If a participant is arrested, reports suicidal ideation, or some other extreme adverse event, a qualified study staff member (i.e., [name] [name], a licensed psychologist) may ask them to withdraw from the study, and if appropriate, refer them to necessary services. According to IRB, if a participant becomes incarcerated while enrolled in a study, all research interactions and interventions with that participant, and the obtaining of identifiable private information about the participant must cease. When participants withdraw from the research, study staff will update their data set to reflect this change. Study team members will no longer contact participants to schedule future study activities, depending on the time point at which the participants withdraw.

Unless participants expressly request the destruction of whatever data that has already been collected, and unless participants request no further data be collected about them whatsoever, study staff may continue to gather certain information at the other time points at which the participants would have been seen had they remained active in the study. Unless otherwise instructed by these participants, study staff may also continue using their previously collected data for analysis purposes.

7.1 Lost to follow up

Participants will be considered lost to follow-up after five failed attempts to contact them. To minimize loss to follow-up and missing data, we will contact participants by phone if they miss intervention sessions. We will ask about barriers to participation and brainstorm ways to facilitate their participation and accommodate their unique circumstances so they can fulfill their participation in the study.

8 RISKS AND BENEFITS

8.0 Risks

Though we regard the risks of participating in this pilot project to be low, we will take care that every member of the research study team is trained to handle all situations with sensitivity and empathy. All research staff is required to complete UM-mandated training on the Protection of Human Research Participants, which must be renewed on a yearly basis. Certificates for all research staff will be kept on file. Since the anticipated risks associated with this pilot are relatively low, and since the potential benefits for participants are significant, the balance of risks-to-benefits seems reasonable to us.

While taking part in this project, participants may be exposed to information related to cancer survivorship and HIV, and they may be asked to discuss sensitive topics, both of which may lead some participants to experience transient, mild anxiety. In these cases, every attempt will be made to provide relief to participants and to ameliorate the source of their discomfort. Should participants experience extreme acute or persisting affective reactions at any point during the study, they will be referred to a psychiatrist or clinical psychologist associated with the study site in question.

In the event that a participant reports symptoms or concerns of extreme distress (i.e., severe symptoms of depression and/or anxiety, suicidality, etc.), the PI will assess the severity of such distress by meeting individually with the participant at an appropriate juncture either after completion of the study activities scheduled for that time point, or potentially immediately, in emergencies. If it is then determined that the participant needs individual care, our research staff will be prepared to refer the patient to an additional source of clinical intervention. Participants may be referred to the appropriate channels within University of Miami health system. They will also be provided with a list of community resources in the Miami area that serve individuals experiencing extreme distress.

In addition, group sessions provide a particular challenge to confidentiality because it is possible that participants may repeat comments outside the group. Research staff will remind participants not to talk to people outside the group about what was said in the group sessions and to keep it confidential. Research staff will ask participants to attend the group sessions alone from a quiet, private, confidential room with no background noise.

There is the potential for participants to be bothered by the questions asked during the final individual interviews, which may make them feel uncomfortable, angry, sad, embarrassed or fatigued.

Lastly, confidentiality during internet communication activities cannot be guaranteed. The study team will provide participants with internet privacy tips and show them how to log in to and use the program. Also, participants will be completing all questionnaires online using a secure and unique log in REDCap (See section 12.6 for Data Handling and Record Keeping).

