4 STUDY DESIGN

4.0 Overall Design

This is a single-arm feasibility trial of a culturally-tailored web-based **SmartManage** (**Stress Management and Relaxation Training Management**) intervention. For this study, staff will utilize these primary avenues for participant recruitment: 1) the University of Miami Medicine system and its University of Miami affiliates (e.g., Sylvester Confidential

Comprehensive Cancer Center, consent to contact lists from other University of Miami investigators), 2) online advertising, via social media, and 3) collaboration with external partnering community-based organizations.

Culturally-Tailored Web-Based SmartManage Intervention: Through our prior work with cancer survivors and HIV+ SMM, we have developed, implemented, published and disseminated evidence-based manuals to managing prostate cancer survivorship or HIV infection in sexual minority men. CBSM is and evidence based, chronic disease management program, from which we derived content for the web-based SmartManage intervention for HIV+ SMM cancer survivors. The web-based SmartManage intervention includes ten 90-minute weekly therapist delivered group sessions (4-6 participants) via video conference. In the first 30 minutes, participants are taught/discuss a new stress reduction technique whereas the latter 60 minutes focus on stress- and self-management. Disease course, symptom burden, communication with intimate partner and/or family members and health care provider, impact of stress on physical and mental health and symptoms, and management of symptom burden and decrements in HRQoL are used for educational purposes and as catalysts for CBSM techniques. Participants describe stressors with an emphasis on symptoms and disruption, HRQoL and their coping responses for in-session role-plays. The SmartManage web platform has all intervention material, resources, and exercises.

We will adapt each of the SmartManage intervention components to be compatible with our participants' cultural beliefs and context by including culturally-relevant content and examples within both the didactic (website) and interactive (session) portions of the SmartManage intervention. Specifically, our intervention will be adapted to reflect the values of familism, allocentrism, health stigma, power distance, external locus of control, and male gender roles. Our adaptation will be guided by previous cultural concepts and adaptations used to inform similar CBSM studies.

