12 SUPPORTING DOCUMENTATION AND OPERATIONAL CONSIDERATIONS

12.0 Informed Consent Process and Documentation

12.0.1 Consent Process

Informed consent is a process that is initiated prior to the individual's agreeing to participate
Confidential

in the study and continues throughout the individual's study participation. The consent process will take place remotely via videoconference on e-consenting using REDCap. Consent forms will be Institutional Review Board (IRB)-approved and the participant will be asked to read and review the document before the videoconference call. At the beginning of the meeting, the research staff will confirm the identity of the potential participant by viewing their driver's license or another form of identification. Then, research staff will explain the research study to the participant and answer any questions that may arise. A verbal explanation will be provided in terms suited to the participant's comprehension of the purposes, procedures, and potential risks of the study and of their rights as research participants. Participants will be given as much time as needed for them to be comfortable with participating in this study. Participants will have the opportunity to carefully review the consent form and ask questions prior to electronically signing. The participants should have the opportunity to discuss the study with their family or surrogates or think about it prior to agreeing to participate. The participant will electronically sign and date the informed consent document prior to any procedures being done specifically for the study. Participants must be informed that participation is voluntary and that they may withdraw from the study at any time, without prejudice. An electronic copy of the informed consent document will be given to the participants for their records. The informed consent process will be conducted, and the form signed before the participant undergoes any study-specific procedures. The rights and welfare of the participants will be protected by emphasizing to them that the quality of their medical care will not be adversely affected if they decline to participate in this study.

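### The distress plan for a remotely run trial names only University of Miami and Miami-area resources, and the supplied text describes no step that records where the man is during a contact

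*Combined protocol and SAP*

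**What the plan says.** **Remote contact.** Section 5.2 describes recruitment as online or by phone, and for men on the contact lists it describes staff "giving the individual the option of completing the full screener either by phone or online." On consent, section 12.0.1 states: "The consent process will take place remotely via videoconference on e-consenting using REDCap." Section 4.0 specifies "ten 90-minute weekly therapist delivered group sessions (4-6 participants) via video conference." Under section 6 the final interview is by phone or videoconference.

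**Who can join.** Sections 5.0 and 5.1 contain no residence criterion. Section 5.2 adds social media, paid referrals from enrolled men, and online platforms. For ResearchMatch it says: "First, we will enter our inclusion criteria to generate a list of potentially eligible participants."

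**Distress and suicidality.** Section 5.1 excludes men who "have overt signs of psychopathology (i.e. psychosis) and/or suicidality at the time of screening." Section 7.0 provides for suicidal ideation during the study: a licensed psychologist may ask the man to withdraw and, if appropriate, refer him to services. In section 8.0 the principal investigator assesses severity in an individual meeting, immediately in an emergency, and staff stand ready to refer to a further clinical source. The named destinations are a psychiatrist or psychologist associated with the study site, University of Miami health system channels, and the local list: "They will also be provided with a list of community resources in the Miami area that serve individuals experiencing extreme distress." Section 12.2 repeats the site clinician and the Miami-area list.

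**The concern.** The trial can enroll men at a distance, but its place-specific resources are those of a local clinic. Two consequences follow, and they are separate.

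- **The list.** A man living elsewhere who reports severe distress would be handed resources for a city he is not in. This concerns non-local men only.
- **The location.** If a man discloses suicidality on a call and the connection drops, staff need to know where to send help. The supplied text does not say that they will have this. It concerns any remote contact, with local men as well, because a man who lives in Miami need not be at home when he joins.

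What is at stake is participant safety in a rare event. No estimate, test or feasibility criterion depends on it.

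**Working it through.** The plan gives no figure to reproduce. The check sets the sections side by side.

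**1. Is any contact with study staff described as in person?** Recruitment and screening (5.2), consent (12.0.1), questionnaires (online, 8.0), sessions (4.0) and the interview (6) are all by phone, video or web. The one qualification is in 5.2: men found by chart review first hear of the study from their treating physician. That is not a contact with study staff, and it concerns University of Miami patients.

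**2. Can a man outside Miami be eligible?** Section 5.0 has 8 inclusion items (a to h) and section 5.1 has 6 exclusion items (a to f): 8 + 6 = 14, of which 0 concern residence. The nearest is access to a device with internet.

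**3. Can he be reached?** The university clinics and contact lists, and the local community organizations, tend toward local men. Social media, ResearchMatch and participant referral state no geographic limit. The ResearchMatch search uses the inclusion criteria, which contain no place.

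**4. Where does the distress plan send him?** Of the named destinations, two are explicitly local: University of Miami channels and the Miami-area list. The site clinician is local by inference, because the Protocol Summary lists the University of Miami Health System as the only enrolling site. The wording in 7.0 and 8.0 on other services is general and names no place.

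**5. Is his location recorded?**

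| Possible source | What the text gives |
|---|---|
| Intake demographics (6) | The items named are "age, race, education, employment status, income, nativity, years in the US, and relationship status"; residence is not among them, but they are given as examples, so the list is not closed |
| Identification at consent (12.0.1) | Viewed to confirm identity; comes after screening; no recording of an address is described |
| Stored contact information (12.1) | Content not specified; it may include a phone number or home address |
| Start of a session (4.0, 8.0) | No location prompt described |

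Even a stored home address would not show where the man is on a given day.

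**6. How many men?** The documents do not say. Enrolled non-local men = 30 × assumed share: 30 × 0% = 0; 30 × 10% = 3; 30 × 30% = 9. The shares are assumptions chosen only to show a range. Men screened but not enrolled would be additional, and their number is not given.

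**The case against.** The strongest reply is that the plan does respond to distress, and that the list is only an extra. This largely stands. The principal investigator's assessment comes first, can be immediate, and is not tied to a place. Staff are committed to being prepared to refer beyond the study, and 7.0 lets a licensed psychologist refer to whatever services are needed. A reader might infer that the protocol confines referral to Miami, or that a distant man would get nothing but a list. The text supports neither.

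A reader might also infer that staff will not know where men are, or that every session will run without a recorded location. That would turn silence into fact. The screener, contact script and data and safety monitoring plan were not available, and consent pages were removed from the supplied text; any of these may hold a location step. Staff on a live call can also simply ask.

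Other replies carry some weight:

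- Suicidality at screening is an exclusion, and the protocol rates risk as low. This lowers the chance of an event during sessions, but 7.0 and 8.0 still plan for one, and screening is itself a remote contact.
- Section 8.0 asks men to join sessions alone from a private room. This protects confidentiality while the man is on live video with a therapist. It does not mean that nobody else is in the home, so it should not be used to enlarge the risk.
- Sections 8.0 and 12.2 speak of participants, a term the protocol also applies to men not yet enrolled. Whether the pathway reaches a man found suicidal at screening is therefore unclear; one cannot say that it does not.

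None of this makes the Miami-area list useful to a man elsewhere, or supplies a described location step.

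**Conclusion.** The point holds as a limited safety gap. The design permits men outside Miami, and the only place-specific resources in 8.0 and 12.2 are local. The supplied text describes no step that records where a man is during a contact. The list is of little use to a non-local man, and staff may lack a location if a connection drops.

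The size cannot be derived: the number of non-local men is unknown and may be zero. The location part does not depend on that number. It rests on the supplied text alone and would fall away if a document not seen here already contains the step; a cross-reference in 8.0 would then suffice. The wording of the list would still need correction. Endpoints, sample size and analysis are unaffected. This is an inexpensive improvement to make, and does not show that the trial lacks a distress plan.

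**What to change.** - **(a) Location.** At the start of every live remote contact (screening call, consent call, video session, final interview), record the man's current physical location and a callback number. Add the same field to the online screener, where a disclosure could arrive with no staff member on the line.
- **(b) Resources.** In 8.0 and 12.2, replace the Miami-only list with resources for the area where the person is, plus a national crisis line.
- **(c) Optional.** State in 8.0 that the assessment and referral pathway also covers men who show suicidality at screening.

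**Cost.** A short IRB amendment, one field on the contact and screening forms, and a resource list kept by area. Location is one more identifier to protect under 12.1. Eligibility, sample size, endpoints and schedule do not change.
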